HCC 10-027: Phase II study for Curative Intent Treatment for Patients with Oligometastatic Disease at Initial Presentation

Protocol version: 02/13/2023

Principal Investigator:

[name]- Assistant Professor
Department of Radiation Oncology
UPMC Presbyterian Shadyside
[contact]
Ph [contact]
[contact]

Statistician

[name]
UPMC Cancer Pavilion [name]
[name],
[name]
[contact]
Ph [contact]

NCT Number: NCT01345539

IND Number Exempt

Table of Contents

Summary	3
1.0 INTRODUCTION.....	4
2.0 OBJECTIVES.....	6
3.0 PATIENT SELECTION.....	6
4.0 PRETREATMENT EVALUATIONS/MANAGEMENT.....	8
5.0 TREATMENT OVERVIEW.....	9
6.0 RADIATION THERAPY.....	9
7.0 DRUG THERAPY.....	11
8.0 SURGERY.....	11
9.0 OTHER THERAPY.....	11
10.0 PATIENT ASSESSMENTS	12
11.0 STATISTICAL CONSIDERATIONS.....	13
12.0 DATA SAFETY AND RECORDING.....	14
REFERENCES.....	19
APPENDIX I - Schedule of events	22
APPENDIX II - Performance status scoring.....	23
APPENDIX III - Guidelines for SRS/SBRT dosing and fractionation	24
APPENDIX IV - Sample of QOL form (FACT-G)	27

Summary

Title: Phase II Study for Curative Intent Treatment for Patients Presenting with Oligometastatic Disease at Initial Presentation

Hypothesis: Patients with oligometastatic disease (defined here as 5 or fewer sites of metastatic disease involving 3 or fewer organ systems) are potentially curable with stereotactic radiosurgery (SRS) or stereotactic radiotherapy (SRT) (collectively referred to as stereotactic body radiotherapy or SBRT) to the metastatic disease sites in combination with standard curative therapy to the primary site.

[figure not shown]
Primary objective: Delivery of SBRT to multiple sites in a safe and effective manner with acceptable toxicity

Primary Endpoints:

- Presence of multiple sites (between 2 and 5 sites)
- Acceptable toxicity: Grade 3 or less

Secondary Objectives/Endpoints:

- Quality of life (as measured by the FACT quality of life surveys, see appendix IV)
- Local control of metastatic sites (with measurable/quantitative assessment): proportion of patients with Complete Response (CR), Partial Response (PR), or Stable Disease (SD)
- Local control of primary site (with measurable/quantitative assessment): proportion of patients with local Complete Response (CR), Partial Response (PR), or Stable Disease (SD)
- Overall survival (OS)
- Two-year Overall Survival
- Analysis of patterns of failure post-SRS/SBRT (subsequent sites of failure and time to failure): proportion of patients with Progressive Disease (PD)

- * oligometastatic disease defined as 5 or fewer sites of metastatic disease involving 3 or fewer organs
- # Only patients with oligometastatic disease at presentation are eligible. Patients with recurrent disease are not eligible for this study.

Patient Population: (See Section 3.0 for Eligibility)

Patients with stage IV (M1) disease at initial presentation (newly diagnosed) who have 5 or fewer sites of metastatic disease involving 3 or fewer organ systems. Patients have not had previous therapy for disease.

REQUIRED SAMPLE SIZE: 44 PATIENTS (SEE SECTION 11.0)

1.0 INTRODUCTION

Death from metastatic cancer is a common cause of death, accounting for 80-90% of cancer deaths (3). The classic thought process is that metastatic disease is incurable and thus treatment, if given, is often palliative. However, it has been reported that a subset of patients with limited volume metastatic disease are in fact curable if given aggressive therapy. This group of patients has become known as "oligometastatic". The concept of oligometastatic disease was established by Hellman in the mid 90's (11, 12). The concept states that there is an evolution or progression of malignant cells through acquired mutations or other mechanisms that allow the cancer to have a step-wise pattern of spread. Cancer cells must first acquire the ability to spread beyond the original disease site, then acquire the ability to establish metastatic lesions (often involving vascularization) and then acquire the ability for further spread. Furthermore, tumor cells may require specific conditions at each step in the process, and that different cancers have different host conditions required for successful metastases, this concept is known as the 'seed and soil' theory (13-14) which explains a step in the process from localized disease to widespread metastatic disease. The step in the process between localized disease and widespread metastatic disease is referred to as "oligometastatic disease". Because oligometastatic disease has not yet acquired the ability for widespread tumor cell dissociation, the sites of tumor burden are limited. In theory, if the primary tumor and the sites of oligometastatic disease could be successfully treated, it would be possible to cure such patients.

This theory has been, in retrospective reviews, shown to be potentially true for numerous cancer types. Patients with limited metastatic disease (oligometastatic disease) to the liver from colon cancer who received aggressive therapy to the liver lesions have had survival rates much better than would be predicted for stage IV disease. Five-year survival rates following liver resection for metastatic colon cancer range between 25% and 55% compared with 0% and 5% for non-operated patients (43). This has also been shown to be true for metastatic disease in bone (29), brain (30), pancreas (1) and lung (31).

Similarly, treatment of the primary lesion in the setting of metastatic disease has been shown to improve survival in breast cancer (33-39), renal cell cancer (40), gastric cancer (41) and melanoma (42). University of Chicago (33) reported 22% long term survival in NSCLC patients presenting with 1-2 metastatic sites treated with aggressive therapy.

While surgical resection has been the first treatment option evaluated in oligometastatic patients, radiation is another viable treatment option. Stereotactic radiosurgery (SRS) and stereotactic radiotherapy (SRT) involve high radiation doses delivered in a very conformal manner. SRS and SRT (collectively known as stereotactic body radiotherapy or SBRT) involve limited radiation to

surrounding normal tissue yet are capable of curative doses of radiation to the primary target. SBRT is well tolerated and can be performed in patients who are not fit for surgery, the mortality of SBRT is exceedingly low, and the number of treatments for SBRT ranges from 1 to 10 making it less burdensome for patients.

SBRT has been evaluated for treatment of oligometastatic disease in multiple sites. Flickinger (15) reported good outcomes for patients with solitary CNS metastatic lesions treated with gamma knife radiosurgery. Similar good outcomes in this setting have been reported by others (44-46).

Multiple reports are available on SBRT for lung tumors. In several series reporting both primary and metastatic lung tumors treated with SBRT (with 3-5 fractions), local control rates have been impressive, ranging from 70% to 90% (34,42,43). Furthermore, toxicity has been mild, most commonly limited to radiographic lung changes. A phase I dose-escalation trial was performed for patients with lung metastases from various primary sites. SBRT dose was successfully escalated to 60 Gy in three fractions with minimal toxicity reported (21). A case series reported 50 patients with lung metastases who were treated at University of Rochester, most of whom (62%) received 5 Gy/fraction for a total of 50 Gy. Up to five targets were treated per patient. With a mean follow-up of 18.7 months local control of treated lesions was obtained in 42 of 49 evaluable patients (83%). Only 2% had grade 3 toxicity (22). Investigators from Japan reported treating 1-2 pulmonary metastases in 34 patients with various primary tumors using 12 Gy fractions to doses of 48 or 60 Gy, at 2 years, 90% of patients were free of local failure. (18). Little toxicity has been reported when SBRT is used to treat peripheral lung tumors, with pneumonitis rates varying from 0% to 10% (19-20).

The role of SBRT for liver lesions was evaluated in a pilot study of 31 patients with a variety of primary tumors, 17 liver metastases in 14 patients were treated with doses of 7.7-45 Gy in 1-4 fractions. Of 13 lesions treated with greater than 20 Gy, only one lesion progressed with a mean follow-up of almost 10 months (23). A phase I multi-institutional trial sequentially escalated doses up to 60 Gy in three fractions. It was reported that the maximum tolerated dose (MTD) was not reached and a single patient out of 36 patients failed in-field at a median follow-up of 19 months (24).

The outcomes of patients treated with SBRT for multiple organ metastases have also been reported. The University of Rochester reported an analysis on 121 patients with 1-5 metastases treated on two consecutive protocols. Patients on both protocols could have had previous therapy for their disease; only 27 patients had oligometastatic disease at initial presentation. The first protocol treated breast cancer patients with limited metastases, in which no brain lesions were treated. The second protocol included patients with cancer from any primary site and limited metastases including a brain primary. After treatment with ten fractions of 5 Gy over 2 weeks (10 fractions), metastatic lesions were controlled 77% of the time at 2 years (25). Milano (5) reported prospective data on breast cancer patients with oligometastatic disease (less than 5 sites) comparing patients treated with SBRT to those receiving only palliative therapy. Four-year survival was significantly improved in SBRT patients (59% versus 0%). University of Chicago (53) reported on a prospective trial in 29 oligometastatic patients (one to five sites and a life expectancy > 3 months, 81% had prior systemic treatment) who had 56 metastatic lesions treated with SBRT (3 fractions ranging from a total dose of 24 to 36 Gy). The authors found a control rate of 56% for treated sites and only 2 patients had grade 3 or higher toxicity.

From the data available, patients with oligometastatic disease appear to benefit in terms of disease control from SBRT. At this point, no one is able to adequately predict which patients have favorable oligometastatic disease and are good candidates for aggressive and potentially curative therapy and which patients are destined to have development of widespread metastatic disease. Some proposed factors for patients likely to proceed to widespread metastatic disease include size and grade of primary tumor, site of oligometastatic disease, and lymph node status. In order to best treat patients, it is important that careful studies be performed to collect clinical information on patients with oligometastatic disease to analyze patient subsets most likely to benefit from treatment.

While disease outcome is certainly an important endpoint, quality of life (QOL) also is of significant importance, especially in patients with metastatic disease that have traditionally thought to

be incurable. It is important that, until aggressive treatment for oligometastatic disease becomes standard of care, careful attention is paid to the quality of life in treated patients. Multiple validated QOL surveys are available for a variety of cancer sites. Collection of such surveys will help to monitor the impact of treatment on QOL.

To our knowledge, there have not been any prospective trials examining the role of aggressive therapy in the treatment of oligometastatic disease only at initial presentation. None of the previously described reports include only patients at initial presentation; the majority of patients in the prospective and retrospective oligometastatic studies have had previous therapy. In order to better evaluate the role of curative therapy in patients presenting with oligometastatic disease we are proposing a prospective study of this patient cohort. Patients with oligometastatic disease (defined for this study as 5 or fewer sites of disease involving 3 or fewer organ systems) will receive SRS/SBRT to all sites of oligometastatic disease and standard curative therapy to the primary disease. The primary objective for this study will be feasibility with the potential for an eventual phase III study. In addition, clinical and translational information will be collected to better stratify patients with oligometastatic disease for future studies.

2.0 OBJECTIVES

Primary objective: Delivery of SBRT to multiple sites in a safe and effective manner with acceptable toxicity

Primary Endpoints:

- Presence of multiple sites (between 2 and 5 sites)
- Acceptable toxicity: Grade 3 or less

Secondary Objectives/Endpoints:

- Quality of life (as measured by the FACT quality of life surveys, see appendix IV)
- Local control of metastatic sites (with measurable/quantitative assessment): proportion of patients with Complete Response (CR), Partial Response (PR), or Stable Disease (SD)
- Local control of primary site (with measurable/quantitative assessment): proportion of patients with local Complete Response (CR), Partial Response (PR), or Stable Disease (SD)
- Overall survival (OS)
- Two-year Overall Survival
- Analysis of patterns of failure post-SRS/SBRT (subsequent sites of failure and time to failure): proportion of patients with Progressive Disease (PD)

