11.0 STATISTICAL CONSIDERATIONS

Primary objective: Delivery of SBRT to multiple sites in a safe and effective manner with acceptable toxicity

Primary Endpoint(s):

- Presence of multiple sites (between 2 and 5 sites)
- Acceptable toxicity: Grade 3 or less

Secondary objectives/Endpoints:

- Quality of life (as measured by the FACT quality of life surveys, see appendix IV)
- Local control of metastatic sites
- Local control of primary site
- Overall survival (OS), Two-year Overall Survival
- Analysis of patterns of failure post-SRS/SBRT (subsequent sites of failure and time to failure)

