11.2 Sample size

Phase II studies are usually small trials, recruiting participants up to about 20, although often a lot less. However, we plan to analyze the data stratified by different primary cancer such as breast, prostate, and etc., since we are trying to detect which patient subsets are most likely to benefit from the proposed treatment. The sample size can be set at approximately 10 for each patient subset in order to have a reasonable estimate of overall survival, local control, and quality of life for each subset. We estimate that most of the patients will have breast, lung, and prostate primaries and that there will be smaller numbers with other primary types. Based on these assumptions, we estimate a sample size of 40 patients and expect a 10% drop-out rate and thus have set an estimated sample size of 44 patients.

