11.3 Data analysis

Two-year survival rate will be calculated for all the patients and each patient subset respectively by using Kaplan-Meier survival analyses, with survival and event times defined from the day of enrollment until either an event or last follow-up. We can compare these two year survival rates with those from the patients using traditional therapy. Median overall survival will also be estimated.

Univariate survival analysis will be performed to identify the statistically significant variables, using Log-Rank test or univariate Cox proportional hazard regression based on the data type of predictor variables. Significant ($P < .05$) variables on univariate analyses will then be tested with multivariate analyses by using Cox proportional hazard regression model (Milano MT, et al., 2007).

Quality of life outcomes will be analyzed by using univariate and multivariate logistic regression successively and the quality of life will be coded as "improved" or "non-improved".

We will also report the entire patient characteristics at initial presentation of oligometastatic disease and characteristics of Long-term (≥ 2 years) survivors by using descriptive statistics.

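### Local control is an undated proportion of patients with no rule for death, and time to failure is named without a method, so both figures mix SBRT effect with follow-up length and mortality

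*Combined protocol and SAP*

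**What the plan says.** Section 2.0, repeated in the Summary, sets out three related secondary endpoints:

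- Metastases: "Local control of metastatic sites (with measurable/quantitative assessment): proportion of patients with Complete Response (CR), Partial Response (PR), or Stable Disease (SD".
- Primary: "Local control of primary site (with measurable/quantitative assessment): proportion of patients with local Complete Response (CR), Partial Response (PR), or Stable Disease (SD".
- Failure: "Analysis of patterns of failure post-SRS/SBRT (subsequent sites of failure and time to failure): proportion of patients with Progressive Disease (PD".

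Section 11.0 lists local control again without a definition, and keeps "Analysis of patterns of failure post-SRS/SBRT (subsequent sites of failure and time to failure" without a method. Section 11.2 justifies about 10 patients per cancer type as giving a "reasonable estimate of overall survival, local control, and quality of life for each subset".

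In Section 11.3 the named estimator is for survival: "Two-year survival rate will be calculated for all the patients and each patient subset respectively by using Kaplan-Meier survival analyses". The same sentence continues with "survival and event times defined from the day of enrollment until either an event or last follow-up". Log-rank and Cox analyses are for survival predictors, and logistic regression is for quality of life. No analysis is named for local control or for failure, and competing risks are not mentioned.

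Section 10.3.4 schedules imaging every three months for two years after therapy, then every six months to year five. Sections 10.3.5 and 10.3.6 define the response categories at a scan. They do not say how a series of scans becomes one category per patient. On CT, progression includes new lesions.

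**The concern.** A response category is a status that changes. Over as much as five years of scans, a patient can be stable at one visit and have progressed at a later one. Unless the plan says which scan counts, the proportion controlled depends on how long patients were followed.

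Death adds a second ambiguity. A patient who dies without local failure may be counted as controlled, left out, or counted as a failure, and the text permits all three. The analyst could choose among them after seeing the data.

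Two uses of the result are at stake. Section 1.0 cites 77% control at two years as background, and an undated proportion cannot be set against a dated one. Section 11.2 wants estimates by cancer type, to find which patients benefit. The eligible cancers in Section 3.1.2 range from prostate and breast to pancreas and small-cell lung, so mortality can be expected to differ between subsets.

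**Working it through.** **The plan's own figures.** 40 × 1.10 = 44, as stated in Section 11.2 (40 / 0.90 = 44.4 would round up to 45). Neither depends on how local control is defined. The plan states no target for local control or failure, so there is nothing further to reproduce. What follows is an illustration.

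**Inputs.**
- C = 0.77, control at 24 months (Section 1.0). It is a per-lesion figure, used here per patient and taken as control in the absence of death.
- S = survival at 24 months. The documents give none, so I assume 0.50 and vary it from 0.10 to 0.90.
- Constant, independent hazards of local failure and death (assumption).

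**Formulas.** λ = −ln(C)/24 and μ = −ln(S)/24 per month. By month t:
- failed: F = λ/(λ+μ) × [1 − exp(−(λ+μ)t)]
- died without failure: D = μ/(λ+μ) × [1 − exp(−(λ+μ)t)]
- alive without failure: A = exp(−(λ+μ)t)

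With C = 0.77 and S = 0.50, λ = 0.01089, μ = 0.02888, λ+μ = 0.03977 and λ/(λ+μ) = 0.2738.

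**Step 1: follow-up length, deaths without failure counted as controlled (1 − F).**
- 3 months: 1 − 0.2738 × (1 − 0.8875) = 96.9%
- 24 months: 1 − 0.2738 × (1 − 0.385) = 83.2%
- 60 months: 1 − 0.2738 × (1 − 0.092) = 75.1%

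**Step 2: death rule at 24 months.** F = 0.168, D = 0.447, A = 0.385.
- Deaths controlled: A + D = 83.2%
- Deaths excluded: A/(A + F) = 0.385/0.553 = 69.6%
- Deaths as failures: A = 38.5%

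**Step 3: direction of the mortality effect at 24 months, same C.**
- S = 0.10 (F = 0.094, A = 0.077): 91% if deaths are controlled, 0.077/0.171 = 45% if excluded.
- S = 0.90 (F = 0.219, A = 0.693): 78% if deaths are controlled, 0.693/0.912 = 76% if excluded.

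Higher mortality raises the figure under the first rule and lowers it under the second.

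**Step 4: response to SBRT effect.** At 24 months with S = 0.50 and deaths counted as controlled, true control of 56%, 77% and 90% reads 67.2%, 83.2% and 92.7%. The 56% is the undated per-site rate cited in Section 1.0, treated here as a two-year rate.

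**Step 5: subset size.** With 10 patients, expected local failures by 24 months are 10 × F = 0.9, 1.7 and 2.2 at S = 0.10, 0.50 and 0.90. An observed 8 of 10 controlled has an exact 95% interval of about 44% to 97%.

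**The case against.** The strongest reply is that time is already in the plan. Time to failure is named in Sections 2.0 and 11.0, Section 11.3 speaks of event times running to an event or last follow-up, and dated scans are scheduled. This is correct, and it would be wrong to say that the plan ignores time for failure. But the event is never tied to local failure, the only summary given is a proportion with progression, and deaths are not dealt with. For the two local-control endpoints even the word time is absent.

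A reader might infer that the reported figure reflects follow-up and mortality instead of SBRT. Step 4 shows otherwise: the figure is confounded, but it still moves with SBRT effect.

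A reader might also infer that early death always flatters control, so that a rapidly fatal cancer looks better controlled than an indolent one. Step 3 shows that this holds under one death rule and reverses under another. The documents state neither rule, so no direction can be claimed.

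The 3-month figure supposes an early read-out that no section plans. It marks the end of a range and is not a forecast. Nor is it a contradiction that a patient may be locally controlled and yet count as progressed: CT progression includes new lesions, so the endpoints measure different things.

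Finally, no test or decision rule uses local control, and sampling error in a subset of 10 is larger than most of these shifts. That limits the severity. It does not define the endpoint.

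**Conclusion.** The concern holds in a limited form. Local control at the metastases and at the primary is not defined well enough to yield a single number, and time to failure lacks an event definition, an estimator and a death rule. Under the stated assumptions one SBRT effect reads anywhere from 75% to 97% by follow-up length, and from 39% to 83% at 24 months by death rule. The result cannot be compared across subsets or with the cited two-year figure. That last comparison has a further obstacle, since 77% is per lesion and the endpoint is per patient.

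The percentages rest on constant independent hazards, the per-lesion input and an assumed survival. They show sensitivity and predict nothing about this trial.

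Two further inferences are not supported. Cumulative incidence does not remove mortality differences between subsets: the 91% and 78% in Step 3 are exactly one minus the 24-month cumulative incidence. And the trial's main conclusion is not affected, because the endpoints are secondary and the sample size of 44 and the primary toxicity endpoint stay as they are. Severity: should-fix.

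**What to change.** In Sections 2.0, 11.0 and 11.3, replace the three proportions with three times measured per patient from enrollment:

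1. to first local failure at a treated metastatic site (new lesions elsewhere do not count as local failure);
2. to first local failure at the primary;
3. to first failure at any site.

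Include all treated patients, treat death without failure as a competing event, and censor at the last adequate scan. Report cumulative incidence with 95% confidence intervals at 12 and 24 months. Do not simply extend Kaplan-Meier to failure with deaths censored: in the illustration that gives 1 − 0.77 = 23% failure at 24 months, against a cumulative incidence of 17%.

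Because cumulative incidence varies with mortality, state that differences in it between subsets will not be read as differences in SBRT effect. Base any such comparison on the cause-specific hazard and, at about 10 patients per subset, label it descriptive. Keep the CR, PR, SD and PD categories as description only.

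The cost is protocol wording and slightly more analysis; the scans are already scheduled. The reported rate may move in either direction, depending on how long patients have been followed and how deaths would otherwise have been counted.
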